Oxytocin and addiction. There is considerable interest in the role OT may play in neuropsychiatric disorders, including substance use disorders^[47]. Importantly, the mesolimbic DA and opioid systems, which are key substrates involved in drug reward and addiction, interact with the OT system during development of tolerance and dependence^[1]. Drug tolerance and compulsive drug seeking involve associative learning and memory processes, which are also regulated by OT systems. Of high significance, recent preclinical data show that OT administration disrupts biobehavioral adaptions associated with long-term alcohol exposure^[2]. In rats, OT reduces development of rapid tolerance to the hypothermic, hypnotic, and myorelaxant effects of alcohol, and produces a prolonged decrease in withdrawal symptoms^[2, 48-53]. OT decreases alcohol preference and produces long-term suppression of alcohol self-administration in rats^[54, 55]. The potential of OT as an AUD treatment is highlighted by a recent small clinical trial in alcohol dependent subjects^[56]. All subjects underwent alcohol detoxification with PRN administration of the benzodiazepine (BZ) lorazepam and concurrent, randomized intranasal OT or placebo. Compared with placebo, OT decreased withdrawal symptoms and amount of lorazepam needed to alleviate withdrawal during detoxification^[56]. It is unknown whether OT will reduce alcohol withdrawal symptoms when administered alone and whether OT alters subjective and reinforcing alcohol effects in human subjects.

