- Current DSM-V major current mood or anxiety disorder or drug use disorder (excluding alcohol and nicotine; excluding mild cannabis use disorder); in or in need of treatment
- Moderate to severe cannabis use disorder
- Drug use in last 30 days and/or positive urine toxicology screens (excluding marijuana/THC)
- History of seizure disorder or closed head trauma

- History of withdrawal-related seizures or serious alcohol withdrawal symptoms (CIWA ≥ 12)
- HIV positive
- Neuroendocrine disorder
- Any serious medical condition that would place subject at risk or interfere with study participation
- Liver function tests $> 3X$ times normal at screening
- Shipley vocabulary score < 18 and REALM score below 19, corresponding to 5th grade reading level
- Prescription medications in last 3 months that could affect CNS or HPA axis function
- Women who are pregnant, nursing or planning pregnancy cannot participate

6. Drugs/ Substances/ Devices

a. The rationale for choosing the drug and dose or for choosing the device to be used.

Oxytocin/syntocinon: We chose 40 IU to maximize the likelihood of observing OT effects based on evidence of increased cerebrospinal fluid levels after intranasal administration of OT^[111] and vasopressin (a similar peptide to OT), and prior studies showing efficacy of 40 IU OT^[38, 42, 112-114]. Doses as high as 320 IU/day OT have been safely administered, without adverse events^[115, 116]. OT has no known abuse liability and has an excellent safety profile in clinical research settings^[37]. The utility and feasibility of intranasal OT as a medication is supported by its success in clinical trials for the treatment of behavioral deficits associated HPA-axis dysfunction including schizophrenia, anxiety, autism, and Prader-Willi syndrome^[61-64].

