Ethyl Alcohol/Alcohol: Alcoholic beverages are legally sold to adults. The dose of alcohol used in the CAD was selected to bring blood ethanol levels to approximately 0.1% was determined based on our previous studies and a comprehensive literature on administering alcohol to research subjects. This BAC corresponds to about 1 g/kg alcohol. The drink is prepared by IDS using 190 Proof ethanol (95%v/v, 0.775 g/ml Spectrum Chemical); the total alcohol dose is divided over three drinks, prepared by mixing the appropriate amount of pure ethanol with a sweet beverage. Using standardized drinking units, 1 (e.g. (One standard drink is equivalent to 12 ounces of beer, 5 ounces of wine, or 1.5 ounces of 80-proof spirits.), this amount is about 4-5 drinks for men and about 3-4 drinks for women when consumed in over 2-hour drinking episode. This amount is within the limits of the typical drinking episode of participants, and are not expected to produce significant adverse events.

After the AMR, subjects may consume up to up to 5 standard drinks (70g ethyl alcohol) of an alcoholic beverage of their choice (e.g., beer, wine or liquor) during the alcohol self-administration session, and drinking is paced. These amounts are within the limits of the typical drinking episode of participants and also are sufficiently large to promote alcohol-motivated responding.

Use of intranasal OT and alcohol will be under FDA-approval via IND 110,562 (holder [name], Co-I, *amendment submitted to FDA 8/4/14*). Amendment application is uploaded to eIRB protocol.

Nicotine Patch: Active nicotine patch (21 mg) is the standard of care for management of nicotine withdrawal.

b. Justification and safety information if FDA approved drugs will be administered for non-FDA approved indications or if doses or routes of administration or participant populations are changed.

n/a

c. Justification and safety information if non-FDA approved drugs without an IND will be administered.

n/a/

7. Study Statistics

a. Primary Outcome variables:

- Peak scores for CIWA-Ar and Craving Scales for abstinence days 1-3.
- Total and subscale scores on POMs Short at assessment and during the CRU stay
- UFC for abstinence days 1-3
- Peak salivary CORT in the TSST
- Number of drinks earned in the AMR
- Peak drug effect VAS scores and peak increase in heart beats per minute (bpm) in the CAD

b. Secondary Outcome variables:

- Stimulation and sedation subscales of the BAES in the CAD

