- Total score of the SHAS in the CAD
- Total scores for the tension and anxiety subscale of the POMS at assessment, during the TSST, and during withdrawal
- Side effects reported on the SAFTEE during the CRU stay

c. Statistical plan including sample size justification and interim data analysis:

In AUD treatment research, a moderate effect of 30-40% improvement is typical. The primary objective of this protocol is to generate estimates of effect size and variance between the OT and placebo treatment groups that could be used to calculate sample size for a larger scale, Phase III study. We have effect sizes for some of our variables using data drawn from the literature and our prior studies. For our power analyses we set type I error (α) = 0.05 where power ($1-\beta$) = 0.8 for the specified effect size for each outcome measure between the OT and placebo treatment groups (n=12 per group, 24 total). Data from prior small trial^[56] showed the OT group (n=7) had 3-fold lower CIWA-Ar scores and a 40% decrease in craving vs. the placebo group (n=4) on day 1. In our prior study in AUD subjects (n=25)^[117], the mean (SD) peak alcohol craving on day 1 of abstinence was 23.4 (7.9). We have power (0.89) to detect a 40% difference in CIWA-Ar and craving between treatment groups (Aim 1). In a previous study, OT reduced stress-induced salivary CORT by 30%^[38]. Based on our TSST data (n=414), with mean (SD) peak salivary CORT of 0.48 (0.46), we will have power (0.8) to detect a 30% difference in CORT between treatment groups (Aim 2). In our pilot study (n=9), subjects drank an average of 3.1 (1.9 SD) drinks, although the 3 drinkers most similar to those in the proposed study drank a

mean of 5 drinks (2.7 SD). We have power (>0.8) to detect a 30% difference in drinks between groups (Aim 3). In our preliminary data ($n=101$), mean (SD) was 118 (62.8) for VAS scores and +13(6.6) for bpm. We have power >0.8 to detect a 40% reduction in peak VAS and bpm (Aim 4). Thus, our sample size of 24 subjects should be sufficient to detect differences between treatment groups, assuming a moderate effect of OT.

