Participants that have elevated blood pressure that are above safe limits, will be given atenolol . We will initiate system-triggered lorazepam treatment for alcohol withdrawal symptoms if the withdrawal score exceeds the clinical cutoff of CIWA-Ar ≥ 12 or on the advice of the study physician. If the CIWA-Ar score is ≥ 12 the subject is given a 2mg dose of lorazepam, and CIWA-Ar scores are then repeated 1 hour later. If the score remains ≥ 10 then another 2 mg dose of lorazepam is given. Hourly CIWA-Ar scores and lorazepam treatment are repeated until CIWA-Ar score decreases to less than 9 or until a maximum of 4 doses of 2 mg lorazepam are administered; if CIWA is 9 or higher after 4 doses, subject will be removed from the study. Subjects will also be removed from the protocol for seizures, hallucinations, or disorientation. At that point in time, the physician on call will be contacted who will arrange for transfer to the medical service. Individuals who require benzodiazepine treatment and are successfully treated with lorazepam will remain in the study to complete the 3-day withdrawal period, but will not complete laboratory session in order to avoid potential complications and confounds of treatment with benzodiazepines.

To date, we have successfully withdrawn over 98% of our alcohol-dependent subjects without medications requiring protocol termination in studies using a similar population. Exclusion of subjects with a history of alcohol withdrawal complications, and/or high CIWA-Ar scores is a successful strategy to help ensure subject safety in studies of new medications^[118-120].

- v. *Oxytocin administration:* Oxytocin (40 IU/ml, Syntocinon spray, Novartis) and placebo (containing the carrier without the neuropeptide) in identical metered-dose nasal spray bottles (Lukas-Bottles, 5-mL, 0.1 mL/actuation) will be obtained from Pharmaworld, Zurich, Switzerland. Oxytocin will be used in these studies under FDA-approval via IND 110,562. The IND 110,562 is held by our collaborator [name]. This supplier and formulation has been used by [name] in her prior studies. Full information sheets of the nasal spray formulation are uploaded. Oxytocin and placebo will be dispensed by The Johns Hopkins Investigational Drug Services. Throughout the study, subjects will remain on the inpatient CRU, and will complete medication side-effects questionnaires. Forms are reviewed by nurses and study staff.

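### Section 7.c claims power of 0.89 for CIWA-Ar without any CIWA-Ar mean or SD; the figure comes approximately from the craving inputs, and only one-sided

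*Protocol*

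**What the plan says.** Section 7.a opens its list of primary outcomes with "Peak scores for CIWA-Ar and Craving Scales for abstinence days 1-3". CIWA-Ar and craving share that bullet, and no order between them is stated.

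Section 7.c sets out the power basis: "For our power analyses we set type I error (α) = 0.05", with "n=12 per group, 24 total". Whether tests are one- or two-sided is not stated. For Aim 1 it offers two sources. One is a small earlier trial (7 on oxytocin, 4 on placebo), cited for a threefold lower CIWA-Ar and a 40% lower craving score on day 1. The other is the investigators' own study of 25 AUD subjects, in which "the mean (SD) peak alcohol craving on day 1 of abstinence was 23.4 (7.9"). It then concludes: "We have power (0.89) to detect a 40% difference in CIWA-Ar and craving between treatment groups (Aim 1").

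Three other places bear on the CIWA-Ar level to expect:

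- Section 5.b excludes "History of withdrawal-related seizures or serious alcohol withdrawal symptoms (CIWA ≥ 12").
- Section 8.b reports: "To date, we have successfully withdrawn over 98% of our alcohol-dependent subjects without medications requiring protocol termination".
- Section 3 describes the small earlier trial: "All subjects underwent alcohol detoxification with PRN administration of the benzodiazepine (BZ) lorazepam", alongside randomized intranasal oxytocin or placebo.

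**The concern.** One power figure is attached to two outcomes, and inputs are given for only one of them. A power for a relative difference depends on the ratio of SD to mean. That ratio can be computed for craving. For CIWA-Ar it cannot, because a between-group ratio of scores carries no information about spread.

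The source of the CIWA-Ar ratio also differs from the planned sample. It came from 11 alcohol-dependent subjects in detoxification. This trial removes people with a history of serious withdrawal before entry, and section 7.c does not say what CIWA-Ar level or spread is expected afterwards. The earlier ratio may not carry over.

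What is at stake is how a CIWA-Ar result will be read. Section 3 makes a further inpatient trial conditional on oxytocin relieving withdrawal. A null CIWA-Ar result set beside a stated power of 0.89 would look like good evidence of no useful effect, although the true power is unknown and could be far lower.

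**Working it through.** **Inputs.** All are from section 7.c unless marked as assumed: 12 per group; α = 0.05; 40% relative difference; craving mean 23.4, SD 7.9. The test is the two-sample t-test named in the same section, taken with the same SD in both arms.

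**Step 1: reproduce 0.89 from craving.**

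- Difference: 0.40 × 23.4 = 9.36.
- Standardized difference: d = 9.36 / 7.9 = 1.185.
- Noncentrality: d × √(12/2) = 1.185 × 2.449 = 2.90, with 22 degrees of freedom.

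| | One-sided | Two-sided |
|---|---|---|
| Exact t-test power | 0.878 | 0.792 |
| Normal approximation | 0.896 | 0.827 |

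The stated 0.89 lies between the two one-sided values and well above both two-sided ones. As a check on the equal-SD assumption, suppose the SD in the oxytocin arm also falls by 40%, to 4.74. The pooled SD is then √((7.9² + 4.74²)/2) = 6.51, and t-test power is 0.96 one-sided and 0.92 two-sided. That does not give 0.89 either.

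**Step 2: what CIWA-Ar would need.** For a 40% difference, d = 0.40 / (SD/mean), so only the ratio matters. Solving for t-test power of 0.89 with 12 per group:

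- one-sided: SD/mean ≤ 0.33 (d ≥ 1.21);
- two-sided: SD/mean ≤ 0.29 (d ≥ 1.36).

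Craving's own ratio is 7.9 / 23.4 = 0.34. CIWA-Ar would therefore have to be slightly less variable, relative to its mean, than craving. The protocol gives nothing from which to judge that.

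**Step 3: the range if the ratio is larger.** The SD/mean values below are assumptions; the protocol gives none for CIWA-Ar.

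| Assumed SD/mean | d | Power, two-sided | Power, one-sided |
|---|---|---|---|
| 0.34 (as craving) | 1.18 | 0.79 | 0.88 |
| 0.5 | 0.80 | 0.47 | 0.60 |
| 0.7 | 0.57 | 0.27 | 0.39 |
| 1.0 | 0.40 | 0.16 | 0.24 |

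In points, again on assumed values and two-sided:

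- Placebo mean peak 4: a 40% difference is 1.6 points, with power 0.47, 0.24 and 0.16 at SD 2, 3 and 4.
- Mean 8: 3.2 points, with power 0.96, 0.70 and 0.47 at the same SDs.
- Mean 6 with SD 2, or mean 9 with SD 3: 0.80.
- Mean 10 with SD 3: 0.88.

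Plausible-looking assumptions thus span 0.16 to 0.96. The document does not allow a choice among them.

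**The case against.** The strongest reply is that this is an estimation study. Section 7.c says its primary objective is to generate effect sizes and variances for a later trial, and section 3 leaves a full examination of withdrawal to a later inpatient trial in a broader sample. Hypothesis 1a also covers craving, and section 7.c provides for transformation or non-parametric analysis. The planned 40% difference is smaller than the threefold difference cited (a fall of about 67%), so the investigators were not taking the small trial's effect at face value. All of this stands. It limits the harm, but it does not supply the missing CIWA-Ar inputs, and an estimation study has no need of an unsupported power figure.

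A reader might go further and infer that the entry criteria screen out withdrawal altogether, so that CIWA-Ar will sit at its floor. The documents do not support that:

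- Section 5.b removes the serious end only. Subjects must still have AUD, exceed 14 (women) or 21 (men) drinks per week and have a positive PEth.
- The CRU admission criteria in section 4.a use a CIWA-Ar below 9 to decide which unit admits a subject, not whether the subject is eligible.
- Sections 4.a and 7.d plan for in-stay scores of 12 or more, and subjects successfully treated with lorazepam remain through the abstinence days.
- The 98% statement in section 8.b concerns medication leading to termination. It gives no CIWA-Ar distribution.
- As-needed lorazepam is common to the earlier trial and this one, so it is not a contrast between them.

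Nor does it follow that a null result is uninformative when placebo peaks are 8 or fewer. Eight is the upper limit of the protocol's mild band, not a threshold of information: at an assumed mean of 8, two-sided power is 0.70 to 0.96 for SD 3 to 2.

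**Conclusion.** The point holds as a defect in the power statement. The 0.89 has no CIWA-Ar input behind it. It comes approximately from craving alone, and only one-sided; two-sided, craving has power of about 0.79. For CIWA-Ar the claim would be true only if SD/mean were at most about 0.33 (one-sided) or 0.29 (two-sided). With assumed ratios of 0.5 to 1.0, two-sided power is about 0.47 to 0.16. These figures rest on 12 evaluable subjects per group, the same SD in both arms and a t-test.

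The screening adds a caution about carrying over a ratio from 7 versus 4 detoxification subjects. It does not show that CIWA-Ar will fail as an outcome, and it gives no reason to demote it.

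**What to change.** In section 7.c:

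1. Remove CIWA-Ar from the power sentence and present it as an estimation outcome with no power claimed. Alternatively, give a CIWA-Ar mean and SD from a comparably screened sample and recompute.
2. Restate craving power with its sidedness: about 0.79 two-sided, or 0.88 one-sided, for a 40% difference with 12 per group.
3. Plan to report the share of each arm whose peak CIWA-Ar never exceeds 8, as descriptive context for any null result. No decision rule need be attached to it.

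Section 7.a can stay as it is. The cost is wording and one descriptive line from scores already collected; no new data or procedures are needed. The downside is that one stated figure becomes less favourable.

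### The power of 0.8 or more claimed for Aims 2 to 4 does not follow from section 7.c's own means, SDs and 12 subjects per group

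*Protocol*

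**What the plan says.** Section 7.c of the protocol sets alpha at 0.05 and power at 0.8 "for the specified effect size for each outcome measure between the OT and placebo treatment groups (n=12 per group, 24 total"). It then gives a mean, an SD, a percentage effect and a power for each aim:

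- Aim 2, peak salivary cortisol in the stress test: "Based on our TSST data (n=414), with mean (SD) peak salivary CORT of 0.48 (0.46), we will have power (0.8) to detect a 30" per cent difference.
- Aim 3, drinks earned: "In our pilot study (n=9), subjects drank an average of 3.1 (1.9 SD) drinks", and the three pilot drinkers closest to the target population averaged 5 (SD 2.7). The claim is "We have power (>0.8) to detect a 30% difference in drinks between groups (Aim 3").
- Aim 4, response to alcohol: "mean (SD) was 118 (62.8) for VAS scores and +13(6.6) for bpm". The claim is "We have power >0.8 to detect a 40% reduction in peak VAS and bpm (Aim 4").

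The paragraph concludes that "our sample size of 24 subjects should be sufficient to detect differences between treatment groups, assuming a moderate effect of OT". The planned analysis, later in 7.c, is a two-sample t-test or a non-parametric equivalent, with ANCOVA as the adjusted model. Sidedness is not stated. The same section also says: "The primary objective of this protocol is to generate estimates of effect size and variance between the OT and placebo treatment groups".

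**The concern.** The SDs are large relative to the effects claimed. The cortisol SD (0.46) is almost as large as its mean (0.48), so a 30% difference is about a third of an SD, and 12 per group cannot give 0.8 power for that. The drinks, VAS and heart-rate claims have the same problem to a lesser degree.

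All four are primary outcomes in section 7.a, and the stated adequacy of 24 subjects rests on these figures. The results are meant to guide later trials. A reader who believes power was 0.8 may take a null result on Aims 2 to 4 as evidence that oxytocin does nothing, when the study would most likely have missed the stated cortisol or drinks effect.

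**Working it through.** **Inputs**, all from section 7.c: alpha 0.05; n = 12 per group; means, SDs and percentage effects as quoted. Assumptions: equal SDs as stated, raw scale, all 12 per group reach days 4 to 6.

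**Formula.** d = (percentage × mean) / SD. Power comes from the noncentral t distribution with 22 df and noncentrality d × √(12/2) = 2.449 d. The critical value is 2.074 two-sided and 1.717 one-sided.

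**The plan's own figure first.** Aim 1 craving is 23.4 (SD 7.9) with a 40% effect: d = 9.36/7.9 = 1.185. Power is 0.792 two-sided and 0.878 one-sided; the protocol states 0.89. The one-sided version is close (0.896 with a normal approximation), so the authors may have worked one-sided. Both versions are therefore carried through.

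| Outcome | Difference | d | Power, two-sided | Power, one-sided | Stated |
|---|---|---|---|---|---|
| Cortisol, 30% of 0.48, SD 0.46 | 0.144 | 0.313 | 0.114 | 0.184 | 0.8 |
| Drinks, 30% of 3.1, SD 1.9 | 0.93 | 0.489 | 0.209 | 0.315 | >0.8 |
| Drinks, 30% of 5, SD 2.7 | 1.5 | 0.556 | 0.256 | 0.372 | >0.8 |
| VAS, 40% of 118, SD 62.8 | 47.2 | 0.752 | 0.421 | 0.555 | >0.8 |
| Heart rate, 40% of 13, SD 6.6 | 5.2 | 0.788 | 0.455 | 0.589 | >0.8 |

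**What 0.80 power would require.** With 12 per group, d must be 1.197 two-sided or 1.048 one-sided. Multiplying by the stated SD and dividing by the mean gives the required difference.

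| Outcome | Needed difference, two-sided | As % of mean, two-sided / one-sided | Claimed | n per group at the claimed effect, two-sided / one-sided |
|---|---|---|---|---|
| Cortisol | 0.55 | 115 / 100 | 30 | 162 / 127 |
| Drinks (mean 3.1) | 2.27 | 73 / 64 | 30 | 67 / 53 |
| Drinks (mean 5) | 3.23 | 65 / 57 | 30 | 52 / 41 |
| VAS | 75.2 | 64 / 56 | 40 | 29 / 23 |
| Heart rate | 7.9 | 61 / 53 | 40 | 27 / 21 |

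**Other readings tried** (power two-sided / one-sided):

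| Reading | Cortisol | Drinks | VAS | Heart rate | Craving (stated 0.89) |
|---|---|---|---|---|---|
| SD falls with the mean, oxytocin arm only | 0.14 / 0.22 | 0.26–0.33 / 0.38–0.45 | 0.57 / 0.70 | 0.61 / 0.73 | 0.92 / 0.96 |
| SD falls by the same percentage in both arms | 0.18 / 0.28 | 0.37–0.46 / 0.51–0.59 | 0.83 / 0.91 | 0.87 / 0.93 | 0.996 / 0.999 |
| Log-normal scale, CV from stated mean and SD | 0.18 / 0.28 | 0.32–0.38 / 0.44–0.51 | 0.67 / 0.78 | 0.70 / 0.81 | 0.95 / 0.98 |
| 24 per group instead of 24 in total | 0.19 / 0.28 | 0.38–0.47 / 0.51–0.60 | 0.72 / 0.82 | 0.76 / 0.85 | 0.98 / 0.99 |

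The highest values found for Aims 2 and 3 on an unadjusted two-group comparison are 0.29 (cortisol) and 0.62 (drinks): SD reduced in both arms, one-sided, normal approximation. A one-sample formula with n = 24, which is not this design, gives at most 0.44 for cortisol and 0.84 for drinks.

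**The case against.** **Sidedness is unstated and the hypotheses are directional.** That is fair: section 2 predicts decreases, and the Aim 1 figure fits a one-sided test better. But section 7.c tests whether outcomes are different, which reads as two-sided, and one-sided power for Aims 2 to 4 is still only 0.18 to 0.59.

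**Transformation or ANCOVA could raise power.** Section 7.c allows both. On a log scale with a one-sided test, heart rate reaches 0.81 and VAS 0.78, so Aim 4 is a weaker case than Aims 2 and 3. This part stands, but the text declares neither assumption, and the log-scale reading overshoots the Aim 1 figure. For cortisol and drinks the log scale gives at most 0.28 and 0.51. For two-sided power of 0.8, ANCOVA would need a covariate correlation with the outcome of about 0.97 (cortisol), 0.89 to 0.91 (drinks), 0.78 (VAS) and 0.75 (heart rate); none is given.

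**This is a preliminary estimation study, so little turns on power.** Section 7.c does name estimation as the primary objective, and nothing in conduct or analysis has to change. But the same paragraph prints explicit power values and draws a sufficiency conclusion from them, and those statements are wrong on their own inputs.

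**A separate SAP might deal with it.** The claims and their inputs are printed together here, so this is a misstatement rather than an omission.

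**Conclusion.** The concern holds. On the stated inputs, two-sided, the study would miss the claimed cortisol effect about 9 times in 10, the drinks effect about 3 times in 4, and the VAS and heart-rate effects more than half the time. One-sided, the misses are about 8 in 10, 2 in 3, and more than 4 in 10.

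For Aims 2 and 3 the conclusion does not depend on sidedness or on any of the scale or SD assumptions tried. For Aim 4 it is limited to the stated SD on the raw scale; 0.8 is attainable only under undeclared assumptions.

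The figures assume that all 12 per group contribute. Sections 4.a and 7.d end participation before the laboratory sessions for subjects treated with lorazepam, and 7.c makes no allowance for this, so true power can only be lower. Because these are wrong figures on primary outcomes that carry the sample-size argument, they must be corrected.

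**What to change.** In section 7.c:

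1. State sidedness once for all aims and make every power figure match. Two-sided: craving 0.79, cortisol 0.11, drinks 0.21 to 0.26, VAS 0.42, heart rate 0.46. One-sided, if that is intended: 0.88, 0.18, 0.32 to 0.37, 0.56 and 0.59. If other inputs were used (log-scale SD, covariate correlation), print them.
2. Delete the sentence concluding that 24 subjects are enough to detect differences.
3. Rest n = 24 on the estimation objective and give the expected precision. The 95% CI half-width is 2.074 × √(2/12) = 0.847 SD: 0.39 for cortisol, 1.6 to 2.3 drinks, 53 VAS points and 5.6 bpm. Suggested wording: *With 12 per group the study is sized to estimate effect size and variance; if all 12 per group complete, the expected 95% confidence interval half-width for a group difference is about 0.85 SD.*

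The cost is wording only, with no extra subjects and no change to design, outcomes or tests. The price is a less favourable stated power and an openly wide interval: for cortisol the half-width is 0.389/0.48, about 81% of the mean.
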